10 SAFETY ANALYSES

The safety analyses will be based on the Safety population.

10.1 Adverse Events

Adverse events will be coded using the latest Medical Dictionary for Regulatory Activities (MedDRA), and the final version will be stated in the data management plan (DMP). Per protocol, the 28 days after the last dose is the last safety follow up. Therefore, the treatment emergent adverse event (TEAE) is defined as an adverse event (AE) with an onset date on or after the first infusion up to within 28 days from the last infusion date. An AE with missing start date/time will be considered to be a TEAE.

The number (%) of subjects reporting TEAEs in each treatment group will be summarized by system organ class and preferred term; by system organ class, preferred term, and severity; and by system organ class, preferred term, and relationship to study medication. If more than one event occurs with the same SOC/preferred term for the same patient, the patient will be counted only once for that SOC/preferred term using the most severe and most related occurrence for the summarization by severity and by relationship to the study medication.

In addition, number (%) of subjects with treatment-emergent serious AEs (TESAE), number (%) of subjects with non-serious TEAE, number (%) of subjects with most frequent (non-serious) TEAE ($\geq 5\%$), and number (%) of subjects with TEAE leading to discontinuation will be summarized by SOC/preferred term. The hypersensitivity and anaphylactic reactions will be listed.

Listings of subjects with serious adverse events (SAEs), subjects with adverse events leading to discontinuation, and subjects who died will be provided.

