4.4. Study Duration

The Screening Period is up to 2 days prior to randomization, to confirm eligibility.

The Treatment Period is 28 days. Study drug will be administered as IV infusion on Days 1 (day of randomization), 7, 14 and 28.

The Follow-Up Period is 28 days after the last dose.

Visits /assessments will occur every day for 28 days, or until hospital discharge, whichever occurs earlier. If a subject is discharged prior to Day 14 or Day 28, the subject should return as outpatient on Days 14 and/or Day 28, for study drug infusions and assessments. For subjects who cannot return for an in-person visit, study assessments maybe done remotely, such as via phone.

Subjects who discontinue study treatment prior to Day 28 are encouraged to remain in the study to complete all remaining visits and assessments, including for collection of vital status. Subjects

who discontinue treatment, for any reason, will need to return for an Early Treatment Discontinuation visit 28 days (+7 Days) after the last infusion and may be contacted by phone at Day 14 and 28 to check the subject's survival status.

See also Section 5 and 6 for additional detail.

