8.2. Definitions

8.2.1. Definition of an Adverse Event (AE)

An adverse event is defined as any untoward medical occurrence in a clinical trial subject. The event does not necessarily have a causal relationship with study treatment. The investigator is responsible for ensuring that any adverse events observed by the investigator or reported by the subject as defined in the study protocol are recorded in the subject's medical record. The definition of adverse events includes worsening of a pre-existing medical condition. Worsening indicates that the pre-existing medical condition (e.g., diabetes, migraine headaches and gout) has increased in severity, frequency, and/or duration, and/or has an association with a significantly worse outcome. A pre-existing condition that has not worsened during the study or

involves an intervention, such as elective cosmetic surgery, or a medical procedure while on study, is not considered an adverse event.

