8.3. Procedures for Eliciting, Recording, and Reporting Adverse Events

8.3.1. Adverse Event Reporting Period

The safety reporting period begins after the subject has signed the informed consent and ends 28 days after the last dose of study drug. The investigator should notify FibroGen of any death or other SAEs occurring after a subject has discontinued or terminated study participation that may reasonably be related to this study (Section 8.3.5). Pregnancy reporting requirements are outlined in Section 8.3.6.

Adverse events will be followed until resolved, stable, or until the subject's last study visit or subject is lost to follow-up.

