APPENDIX I HANDLING MISSING/INCOMPLETE DATES

A. Handling Missing/Incomplete AE Onset Date

If the AE onset date is incomplete or missing, the following rules will be applied to impute AE onset date.

- If year and month are present, only day is missing,
 - a) If AE onset Year/month = Day 1 Year/month, assign onset day = day of Day 1 (Day 1 is the first infusion day);
 - b) If AE onset Year/month \neq Day 1 Year/month, assign onset day = 1st of the month;
- If year is present, month and day are missing, or when only month is missing (treating day as missing),
 - a) If AE onset year = year of Day 1, assign onset date = month and day part of Day 1 date;
 - b) If AE onset year \neq year of Day 1, assign onset date= January 1st.
- If onset date is completely missing, assign onset date = date of Day 1.

If the stop date is complete and the imputed start date as above is after the stop date, the start date will be imputed by the stop date.

B. Handling Missing/Incomplete Prior or Concomitant Medication Start/Stop Dates

For prior or concomitant medications, including rescue medications, incomplete (i.e., partially missing) start date is imputed the same way as for the AE described above. When the start date and the stop date are both incomplete for a patient, impute the start date first.

Incomplete Stop Date

The following rules are applied to impute the missing stop date, if needed.

- If year is present, month and day are missing, or when only month is missing (treating day as missing)
 - a) If stop year = year of last dose, assign stop date = month and day of the last dose date;
 - b) If stop year \neq year of Day 1, assign stop date= December 31st.
- If year and month are present, only day is missing,
 - a) If AE stop Year/month = Year/month of last dose date, assign stop day = day part of last dose date
 - b) If AE stop Year/month \neq Day 1 Year/month, assign onset day = last day of the month;
- Impute CM end date even if 'ONGOING' is checked so as to report the CM treatment duration in the study if needed.

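### SAP 10.1 defines a TEAE by onset alone, so an AE that starts between consent and first infusion and later worsens on the same record is left out of the TEAE and TESAE counts

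*SAP*

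**What the plan says.** SAP 10.1 takes as treatment-emergent an AE with "an onset date on or after the first infusion" and no later than 28 days after the last one. It adds one inclusive rule for incomplete data: "An AE with missing start date/time will be considered to be a TEAE". Appendix I of the SAP works in the same direction for partial dates; where only the day is missing, "If AE onset Year/month = Day 1 Year/month, assign onset day = day of Day 1". The protocol uses the term TEAE in its safety sections but does not define it, so the SAP wording governs.

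Collection starts earlier than the TEAE window. Protocol 8.3.1 states: "The safety reporting period begins after the subject has signed the informed consent and ends 28 days after the last dose of study drug". Protocol 4.4 sets the length of the gap: "The Screening Period is up to 2 days prior to randomization, to confirm eligibility". Day 1 is both the day of randomization and the day of the first infusion.

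On worsening, protocol 8.2.1 says: "The definition of adverse events includes worsening of a pre-existing medical condition". As amended, protocol 8.3.7 also makes worsened laboratory abnormalities reportable as AEs. Protocol 8.3.2 lists what must be recorded for each AE, including severity and the dates of onset and resolution, and expects investigators to follow reported events until they stabilize or reverse. It does not say what to do when an AE already on record gets worse.

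**The concern.** The subjects are in hospital with an acute respiratory illness, so an event first seen in the day or two before dosing can change grade quickly. The AE list in protocol 8.3.2, with its instruction to follow each event over time, can be read as one record per event. On that reading, an AE that starts at a low grade before the first infusion and becomes severe or serious after it keeps its pre-infusion onset date. It then fails the SAP 10.1 test and drops out of every table built on TEAEs: the overall counts, the severity and relationship tables, the TESAE table and the table of TEAEs leading to discontinuation.

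The SAP is otherwise inclusive. An event with no onset date is counted, while a fully dated event with documented deterioration after dosing is not.

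These tables carry most of the tabulated safety information. SAP 10.2 only lists vital signs, SAP 10.3 reports that no laboratory results were collected, and SAP 10.1 only lists hypersensitivity and anaphylactic reactions.

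**Working it through.** The plan gives no figure to reproduce here; the point is a definition. The check is to apply the rule as written to constructed records, then size one misclassified subject.

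**Inputs.** TEAE window and missing-onset rule: SAP 10.1. Partial-date rule: SAP Appendix I. Start of AE collection: protocol 8.3.1. Screening of at most 2 days: protocol 4.4. Number randomized at termination, 22: SAP 1. The size of each arm and the number dosed are not given.

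**Rule as written.** An AE is a TEAE if its onset is missing, or if first infusion ≤ onset ≤ last infusion + 28 days.

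**Constructed example.** First infusion on 3 July at 14:00 (Day 1); last infusion on 30 July (Day 28).

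1. Onset 1 July, one record, worsens on Day 3 (5 July). 1 July is before 3 July, so it is not a TEAE, whether dates or times are compared.
2. Same event, but the worsening is entered as a new AE with onset 5 July. It is a TEAE.
3. Onset 3 July at 08:00, before the infusion, one record. It is a TEAE if calendar dates are compared (3 July ≥ 3 July) and not a TEAE if times are compared (08:00 is before 14:00).
4. Onset missing. It is a TEAE.

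If the site in case 1 had recorded only the month, Appendix I would set the onset to 3 July and the event would count.

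Cases 1 and 2 are the same clinical course. Only the recording convention separates them, and neither document states that convention for an AE already recorded after consent.

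**Scale.** One subject out of all randomized: 1/22 = 4.5%. If the arms are 11 and 11 (assumption), one subject out of an arm: 1/11 = 9.1%. The safety denominators are subjects dosed, so if fewer than 22 were dosed, one subject weighs slightly more. SAP 10.1 also has a table of non-serious TEAEs with a 5% cut-off and does not say whether this applies overall or by arm. Applied by arm under the 11 and 11 assumption, one subject is enough to decide whether a term appears (9.1% > 5%). Applied overall, one subject alone is not (4.5% < 5%).

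These percentages show what any one misclassified subject weighs. They do not estimate how many subjects are affected. The documents give no count of AEs open at first infusion, and it may be zero.

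**The case against.** The strongest reply is that little falls through the gap.

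- Protocol 8.2.1 makes worsening of a pre-existing condition an AE in its own right. Such an AE would normally be dated from the worsening, and so falls inside the TEAE window. Laboratory worsening is reportable under 8.3.7.
- One record per event is an inference. Protocol 8.3.2 does not forbid a new record, and it tells sites to ask at each visit about changes since baseline or the last visit. SAP 10.1 allows for repeated records of one term in one subject and takes the most severe. The convention may be set in CRF instructions or the data management plan, which are not among the documents.
- SAP 10.1 lists SAEs, AEs leading to discontinuation and deaths without restricting them to treatment-emergent events, and SAP 5 puts all collected data in listings.
- Missing onsets, and partial onset dates that match the Day 1 month or year, are counted as treatment-emergent.
- SAP 5.1 plans no treatment comparison, so no test is affected.

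All of this stands as a limit on scope and size. None of it supplies the missing clause. For an AE that first arose after consent, is still open at first infusion and stays on one record, SAP 10.1 gives the wrong classification, and nothing elsewhere in the SAP or protocol corrects it.

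**Conclusion.** The gap in the definition is certain from the text; its effect is conditional and small. It requires an AE that begins in a window of at most about 2 days, is open at the first infusion, later increases in severity or becomes serious, and is kept on its original record. Where that happens, the TEAE and TESAE tables can understate the event. Where sites opened a new record, the effect is nil.

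Two stronger readings are tempting and are not supported. A reader might infer that illness present at entry which deteriorated on treatment, including the COVID-19 disease itself, is excluded. Protocol 8.2.1 points the other way, since that worsening is an AE that would normally have post-infusion onset. A reader might also infer that serious events are hidden from the safety review. They remain in the listings, and only the summary counts are exposed. Nor do the documents show that any event has been miscounted.

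Severity: minor. The 4.5% per subject rests on 22 randomized; the 9.1% rests on an assumed equal split.

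**What to change.** In SAP 10.1, define a TEAE as an AE with onset on or after the first infusion, or with earlier onset and an increase in severity or a change to serious on or after the first infusion, in both cases up to 28 days after the last infusion. State in the same sentence whether onset is compared by date or by date and time. Query the few AEs ongoing at the first infusion for the date of any worsening.

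The text change is one clause. The real cost is a few retrospective site queries in a terminated study, because if worsening was kept on the original record, its date may not be in the database and the new clause could not be programmed without it. If sites already opened new records, the clause does not inflate the counts, because SAP 10.1 counts a subject once per term.

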8.3.2. Adverse Event Eliciting/Reporting

During the AE reporting period, study site personnel will actively seek information from each subject at each visit to collect any AEs occurring since the previous visit. All AEs will be collected in response to a general question about the subject's well-being and any possible changes from the BL or previous visit. There will be no directed questioning for any specific AE. This does not deter the site from collecting and recording any AEs reported by the subject to site personnel at any other time.

Whenever possible, diagnoses should be recorded when signs and symptoms are due to a common etiology, as determined by qualified medical study staff. The investigator is responsible for reviewing laboratory test results and determining whether an abnormal value in an individual study subject represents a clinically significant change from the subject's baseline values. In general, abnormal laboratory findings without clinical significance (based on the investigator's judgment) are not to be recorded as adverse events. However, laboratory value changes that require treatment or adjustment in current therapy are considered adverse events. Where applicable, clinical sequelae (not the laboratory abnormality) are to be recorded as the adverse event. The investigator is expected to follow reported adverse events until stabilization or reversibility.

The following attributes must be assigned to each AE:

- Description (Investigator's verbatim term describing the event)
- Dates of onset and resolution
- Severity
- Relationship to study drug
- Outcome
- Action taken regarding study drug
- Other treatment required
- Determination of "seriousness"

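### SAP 10.1 and Appendix I.A disagree on whether an AE with no onset date that ended before the first infusion is treatment-emergent (minor)

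*SAP*

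**What the plan says.** SAP 10.1 defines a TEAE by its onset: an AE "with an onset date on or after the first infusion up to within 28 days from the last infusion date". The next sentence, which ends that paragraph, adds "An AE with missing start date/time will be considered to be a TEAE". It makes no exception for a known stop date and does not refer to Appendix I.

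SAP Appendix I.A states its scope as "If the AE onset date is incomplete or missing, the following rules will be applied to impute AE onset date". For a wholly unknown onset it says "If onset date is completely missing, assign onset date = date of Day 1", and it identifies Day 1 as the first infusion day. It then adds a cap for records with a complete stop date: where "the imputed start date as above is after the stop date, the start date will be imputed by the stop date".

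AEs can be recorded before dosing. Protocol 8.3.1 says "The safety reporting period begins after the subject has signed the informed consent and ends 28 days after the last dose of study drug", and Protocol 4.4 says "The Screening Period is up to 2 days prior to randomization, to confirm eligibility". The Schedule of Assessments also marks adverse events at screening.

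**The concern.** An AE that had stopped before any study drug was given cannot have emerged on treatment, whatever its unknown onset date was. The Appendix I cap respects that. The 10.1 sentence, read literally, does not. Because the SAP gives no order of operations, two programmers could each follow it faithfully and classify the same record differently.

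The AE summaries are where this would show. SAP 10.2 only lists vital signs and SAP 10.3 reports that no laboratory results were collected, so the AE tables, nearly all of them restricted to TEAEs, are the only tabulated safety results. At stake is whether those tables can be reproduced, and whether an event known to have ended before the first infusion could be counted in them.

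**Working it through.** The plan states no figure on this point, so the check is one of logic. Apply each rule to the same records and compare.

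**Inputs**
- TEAE window (SAP 10.1): first infusion date ≤ onset ≤ last infusion date + 28 days.
- Default (SAP 10.1): start missing → TEAE.
- Imputation (SAP Appendix I.A): onset fully missing → onset = Day 1. If the stop date is complete and earlier than that, onset = stop date.

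**Illustrative dates (assumed).** Day 1 = 15 July 2020. The last infusion, on Day 28, is 11 August 2020. The window therefore runs from 15 July to 11 August + 28 days = 8 September 2020.

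**Fully missing onset**

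| Stop date | Onset under Appendix I.A | In the 10.1 window? | Literal 10.1 default | Agree? |
|---|---|---|---|---|
| 14 July (day before Day 1) | 14 July (capped) | No: not a TEAE | TEAE | **No** |
| 15 July (Day 1) | 15 July | Yes: TEAE | TEAE | Yes |
| 19 July (Day 5) | 15 July | Yes: TEAE | TEAE | Yes |
| None recorded | 15 July | Yes: TEAE | TEAE | Yes |

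Moving Day 1 to 1 July 2020 gives the same pattern. In the first row the cap sets onset to 30 June, again one day before the window opens.

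The rules therefore part only where the cap moves the imputed onset before Day 1, which needs a complete stop date before Day 1. Everywhere else the Appendix I default and the 10.1 sentence give the same result.

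**How many records could qualify.** Three conditions must hold together: no onset date at all, a complete stop date, and a stop before the first infusion. Reporting starts at consent and screening lasts up to 2 days, so the AE must have ended within that short interval. The documents give no count of missing onset dates and no count of AEs before dosing, so the number affected cannot be calculated.

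**The case against.** The strongest reply is that there is no conflict if Appendix I is applied first. No onset date is then left missing, the 10.1 sentence merely restates the Day 1 default, and an AE that ended before the infusion falls outside the window as it should. That reading is as available as the literal one, and it may be what was intended. What remains is that the SAP does not say so. The inconsistency is unresolved rather than settled either way.

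The second reply is that the record type is close to hypothetical. Protocol 8.3.2 lists "Dates of onset and resolution" among the attributes that must be assigned to each AE, and Protocol 11.3 has incomplete data queried with the site. This stands, and it is the main reason the point is minor.

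The third reply is that counting undatable AEs as treatment-emergent is a cautious convention, that SAP 5.1 rules out treatment comparisons, and that SAP 5 puts all collected data in listings, where the early stop date would remain visible. This also stands. The objection is only to using the default when the stop date already settles the matter.

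A reader might go further and infer that 10.1 overrides Appendix I. Neither section states any precedence, so the documents do not support that.

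A reader might also infer from the words date/time in 10.1 that an AE with a known date before dosing but no clock time becomes a TEAE. That is strained. The definition just before it turns on the onset date, Appendix I.A deals only with dates, and the protocol asks only for dates. On that reading every AE recorded by date alone would be a TEAE and the window would do nothing.

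**Conclusion.** The point holds as a minor inconsistency. SAP 10.1 and Appendix I.A give opposite classifications for one record type: a fully missing onset with a complete stop date before the first infusion. No order of application is stated. The literal 10.1 result is wrong for that record, because the event ended before study drug. For all other fully missing onsets the rules agree.

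The practical size is probably very small and may be nil, since the documents do not show that any such AE occurred. The analyses are descriptive, so no test, power or error rate changes.

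Two stronger inferences should be resisted.
- **Table percentages.** If the 22 randomized subjects split evenly (an assumption), one subject is 1/11 = 9.1% of an arm; with 8 or 14 in an arm it would be 12.5% or 7.1%. Any arm of 20 or fewer puts a single subject at or above the SAP's 5% cut-off for frequent events (1/20 = 5.0%). But this is true of any single AE in a trial this small, so it says nothing specific about this rule. The size of the Safety population by arm is not given either.
- **Partial onset dates.** If missing in 10.1 were taken to include partial dates, more conflicts would appear. One example is an onset known only to an earlier month, which Appendix I places before Day 1. But Appendix I itself separates incomplete from missing dates, so 10.1 need not be read that way. This is a reason to make the wording explicit, not evidence of a wider error.

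**What to change.** Replace the last sentence of the TEAE definition paragraph in SAP 10.1 with:

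*Missing or partial onset dates are first imputed by Appendix I, and TEAE status is set from the recorded or imputed onset date using the window above (first infusion through 28 days after the last infusion). An AE whose complete stop date is before the first infusion date is not treatment-emergent.*

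This keeps the cautious Day 1 default for every other fully missing onset and settles how partial dates are handled. It also retains the upper limit. A replacement that dropped that limit would turn AEs starting more than 28 days after the last infusion into TEAEs.

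The cost is this replacement wording and a small change to the derivation code. The downside is a possible very small fall in the TEAE count. A listing of AEs with no onset date and a stop date before the first infusion would show whether any fully-missing-onset record is affected.
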